For participants who are under 18 years, where their legal guardian(s) gives consent, the participant will be informed about the study to the extent possible given his/her understanding. If the participant is capable of doing so, he/she will be required to indicate agreement by personally signing and dating the written informed consent document. Participants who turn 18 years during the study period will be required to re-consent.

The ICF used will comply with the International Conference for Harmonization of Technical Requirements for Pharmaceuticals for Human Use (ICH) Good Clinical Practice (GCP) guidelines and regulatory requirements.

Information about common side effects already known about iron supplements, can be found in the protocol. This information will be included in the participant informed consent and will be discussed with the participant during the study as needed. Any new information about this drug that is relevant to this study will lead to an update to the informed consent which will then be discussed with the study participants.

- Confidentiality of Study Participants

At study entry each potential blood donor will be assigned a unique study identification number (Study ID). To maintain confidentiality, study specific ID numbers will be used on all samples and related documentation ensure anonymity (samples will be coded with a distinct identifier to ensure the laboratory is blinded). Participants' privacy will also be maintained using standard operating procedures that are already in place at the National Blood Service for engaging with blood

donors. Briefly these involve interviewing and counseling participants in a private area or by phone after confirming their identity, using a pre-defined procedure.

Standardized questionnaires administered by trained interviewers will be used to collect demographic and clinical information from all study subjects into an electronic form directly linked to a password protected database. This database can only be accessed by investigators or study staff designated by the Principal investigators. Paper consent/assent forms which as a matter of necessity have participant names or initials and signatures on them, will be stored securely in a locked cabinet at the study site and accessible only to the principal investigators. These will be stored for 3 years after study procedures, primary analyses, study publications are completed. They will be destroyed by agencies that provide such services. The data collection on all study subjects will conform to requirements of international legislation on data protection. Databases will be password protected. The electronic databases will be kept for a minimum of 5 to 10 years after completion of study reports and publications. No study participant will be identified in data collection, publication, meeting abstract or report derived from the study results or the information collected. Regular data backups will mitigate against risks of fire/flooding. All personnel who handle any personal data will be required to undertake and maintain Good Clinical Practice (GCP) and Human Subjects Protection (HSP) training.

- Regulatory Oversight

Before initiating this trial, we will obtain approval/favourable opinion from the Steering Committee, DCC, PRC/ NHLBI and IRB/IEC for the trial protocol, written ICF, consent form updates, participant recruitment procedures and any other written information to be provided to study participants. Prior to study start, all of the instructions and procedures found in this protocol will be read and accepted by study team. An inspection of the clinical site (site initiation visit) will be done by NHLBI (or a designated representative) before start of study. This visit may be virtual due to the ongoing COVID-19 pandemic.

Monitoring will occur in coordination with the DCC, the PI and an independent DSMB. Regulatory requirements and site level interim monitoring will be tracked by the DCC. The PI will ensure the required documentation is available to the DCC and site monitoring personnel. The US National Heart, Lung, and Blood Institute (NHLBI) will be responsible for providing program oversight through an independent DSMB.

Study initiation and site initiation

This pilot study will be registered on clinicaltrials.gov by the DCC prior to enrolment into the trial.

The principal investigator will ensure the required documentation has been submitted to the DCC for each site participating in this pilot study. This includes:

- A federal-wide Assurance (FWA) number and expiration date
- The required IRB numbers linked to the FWA.
- The required IRB approval letters (original letter and an English translation if not in English and a Translation Verification Statement in the latter case)
- Approved site consent (if different from overall consent, and if not in English, an English translation, and a Translation Verification Statement)
- Information on the investigator of record (name, contact information, completion date of HSP training, completion date of Good Clinical Practice (GCP) training, a signed investigator of record form, and a signed curriculum vitae).
- Medical license of investigator of record
- Information on sub-investigators (name, contact information, completion date of Human Subjects Protection (HSP) training, completion date of GCP training, and a signed curriculum vitae)
- Information on study coordinator (name, contact information, completion date of HSP training, completion date of GCP training, and a signed curriculum vitae)

Laboratory reference ranges (and if available online, URL).

Data collection towards the objectives of this pilot study will not be initiated until the required documentation has been reviewed by the DCC and a site activation letter has been issued to the site investigator of record and the protocol PI.

Interim site level monitoring

In addition, all individuals participating in this pilot study will need to sign an ICF. All study sites will maintain a copy of the ICF for all participants at that study site. Any individuals who are less than 18 years old will have an ICF signed by a parent or other representative with required assent as needed. Upon a site monitoring visit, study data and case report forms will be made available to site monitoring personnel.

REFERENCES

1. Reddy, R. (2012). Blood donation patterns and challenges in Southern Africa. *ISBT Science Series*, 7(1), 296–299. <https://doi.org/10.1111/j.1751-2824.2012.01576.x>
2. WHO. (2017). *Current Status on Blood Safety and Availability in the WHO African Region: Report of the 2013 Survey*. World Health Organization. <https://www.afro.who.int/sites/default/files/2017-06/9789290233480-eng.pdf>

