The WHO advocates the use of repeat voluntary blood donations since these are associated with both blood safety and availability. However, in the absence of adequate interventions to prevent anaemia, repeat attempts by previously iron deficient blood donors leads to IDA and deferment at subsequent donations. The prevalence of anaemia among men globally is 12.7% whilst that of women in reproductive age is 30.2%⁶. The prevalence of anaemia in Ghana is higher than the global average, estimated at 42.4% in women of reproductive age⁷ and 18.8% among peri-urban men⁸.

This high prevalence of anaemia in the general population may contribute to an increased rate of deferrals due to anaemia in potential blood donors in Ghana. This results in a loss of valuable members of the donor pool who could have been retained if they had been identified, counseled, and treated appropriately for iron deficiency and iron deficiency anaemia.

Aim

To determine the potential for iron supplementation and nutritional counseling strategy to increase blood donations in Ghana.

HYPOTHESIS: Haemoglobin levels among deferred blood donors with anaemia will improve to near normal after iron supplementation compared to those who were not deferred with normal haemoglobin.

Objectives

Primary Objectives

The primary objective of this study is to determine the potential for an iron supplementation strategy to increase blood donations in Ghana. To determine this potential, the study will investigate the feasibility and acceptability of this intervention along with key return blood donation measures among first-time blood donors deferred for low haemoglobin or found to have IDA or be ID within the

catchment areas of the SZBC. These aspects of the potential for this intervention will be operationalized as follows:

- **Feasibility** of recruitment, enrolment, retention, and adherence will be evaluated with a target retention rate $> 90\%$ of all participants recruited completing the trial. If we are unable to achieve this target, alternative strategies will be considered for the UH3 phase.

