This pilot study has 2 components: 1) a cross-sectional assessment designed to estimate the prevalence of anaemia leading to donor deferral, the prevalence of ID and the prevalence of IDA among first-time donors, and 2) a longitudinal 2-arm parallel groups trial among first-time voluntary donors that compares haemoglobin levels at 4 months among those with ID or IDA who receive iron supplementation to those without ID or IDA who do not receive iron supplementation. The primary outcome will be haemoglobin levels at 4 months. Participants will be followed for a total of 6 months with study visits at 2, 4 and 6 months after the baseline assessment. Blood draws for FBC, peripheral film comment, Malaria rapid test and ferritin assessment and the administration of a structured questionnaire will occur at all follow-up visits.

The parallel group's component is designed as a non-inferiority trial for haemoglobin levels at 4 months. At baseline, the 2 groups will be determined based on the need for iron supplementation: all individuals with ID or IDA, who satisfy our eligibility criteria regardless of deferral status, will receive iron supplements while all others will not. While a high prevalence of ID and IDA is expected, enrolment will be staggered so that an equal number of participants from each group are enrolled from each site with at least 1 participant who is found to be ID or have IDA. If there are more potential participants in one group at some site, randomization will be used to select the individuals to enroll in the trial to maintain balance over time. The extent of adherence is a central question for this study, and it is also unclear if the haemoglobin deficiency can be improved above what is seen in the control group, hence it is not hypothesized that those receiving

iron supplementation will have higher levels of haemoglobin at 4 months. The hypothesis about iron supplementation intervention is that it will improve haemoglobin levels to near that seen among those who were not deferred. If haemoglobin levels are higher in those receiving iron supplementation the intervention would also be deemed a success. Hence a non-inferiority trial is most appropriate for this hypothesis.

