Selection of the margin is a critical component of a non-inferiority trial. Here, we specify a margin of 1 g/dL for haemoglobin levels at 4 months. Under a collection of reasonable assumptions, this margin will ensure that the majority of those with low haemoglobin at baseline will have haemoglobin levels at 4 months above the threshold for anaemia and should therefore qualify as donors. To see this, assume that half of donors are anaemic at baseline (using the thresholds for anaemia of 13 g/dL for men and 11.5 g/dL for women). A simple calculation finds that if we assume haemoglobin levels are normally distributed (which is a reasonable assumption based on observed distributions for haemoglobin in healthy individuals) and the standard deviation of baseline haemoglobin levels is 1.89 g/dL (this estimate will be described below) then the mean haemoglobin level among men who are deferred is 11.5 g/dL and the mean haemoglobin level among men who are not deferred is 14.5 g/dL (these values for women are 10.0 g/dL and 13.0 g/dL). If we assume that the haemoglobin level among those who are not deferred is the same 4 months later then a margin of 1 g/dL implies a mean haemoglobin level among those with anaemia at baseline of at least 13.5 g/dL for men and 12.0 g/dL for women. Thus, the mean haemoglobin level after 4 months of iron supplementation among those who should have been deferred will exceed the threshold for anaemia and consequently, if the distribution of haemoglobin levels is symmetric, the majority of those who were anaemic at baseline would qualify as donors (in fact at least 60.4% would pass the threshold for both sexes if this distribution is normal). Note that the threshold for the copper sulphate test used for women is 12 g/dL, not 11.5 g/dL, so under these assumptions 50% of women would pass the copper sulphate test. Nonetheless, since well over 50% of donors are men the majority of deferred donors would pass the copper sulphate test. It is

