Out of the sampling frame, participants will be purposively sampled for Focus Group Discussions (FGDs). In all there will be ten FGDs i.e. two groups (male-only and female-only) randomly selected to represent each of the five NBSG voluntary blood donation categories (excluding mass/media event donors), and with each group composed of both first-time and repeat donors. In-depth interviews will also be conducted with blood donation staff and medical officers responsible for blood donation.

Regimen

The prevalence study will be conducted over the first 6 months of the study period. For the cross-sectional deferral assessment, all donation attempts and deferrals from sites where recruitment for the parallel groups study will take place will be recorded. The number of deferrals among first-time donors will also be determined. Potential first-time donors will be asked if they are interested in participating in a study of the prevalence of ID and IDA and the impact of iron supplementation on haemoglobin levels and repeat donation. Those who express interest and consent to the study will be asked to return in approximately 2 weeks. During this 2-week period a full blood count (FBC) and plasma ferritin measurement will be determined, and participants will be classified as ID, IDA or otherwise (which we refer to as controls in this protocol). Those found to be ID or IDA will receive oral

iron supplementation and nutritional counseling. Controls will not be given iron supplementation but will receive the standard practice of nutritional counseling for blood donors. Additional baseline data will be collected at the 2-week return visit. The duration of the intervention period is 4 months with two interim visits (approximately 2 months apart) and a final visit at 6 months. A blood draw will be conducted for a FBC, peripheral film comment, malaria rapid test and ferritin measurement at both interim visits and the final visit. Participants will receive bi-weekly follow-up phone calls for adherence and monitoring for adverse events. Qualitative assessment of acceptability of oral iron supplementation among donors previously deferred will be performed during the final month of the pilot study.

Inclusion Criteria

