Anaemia is a state in which the amount of red blood cells (RBCs) is insufficient to meet the body's physiologic needs ²⁴. Mild anaemia is defined as Hb ranging from 11-12.9 g/dL in adult males and 11-11.9 g/dL in adult females. Moderate anaemia is defined as Hb level of 8-10.9 g/dL and severe anaemia is defined as Hb level of less than 8 g/dL for all the age groups ^{25,26}.

Following FBC and plasma ferritin estimation, screened participants will be classified by the WHO criteria as shown in Table 4:

Table 4: Definition of Iron Status Criteria

| Haemoglobin concentration, g/dL | Plasma ferritin concentration µg/L | Interpretation |
|--|------------------------------------|---|
| [Male] >13.0 [Female] >11.5 | < 15 | Iron deficiency without anaemia |
| [Male] ≥8.0-13.0 [Female] ≥8.0-11.5 | < 15 | Iron deficiency with mild to moderate anaemia |

| | | | |
|-------|------|------|-------------------------------------|
| [All] | <8.0 | < 15 | Iron deficiency with severe anaemia |
|-------|------|------|-------------------------------------|

Schedule of Assessments (Table 5)

| Assessment | Screening (Day -14 to 0) | Enrolment (Day 0) | Biweekly (Throughout) | Interim Visit 1 | Interim Visit (Week 8-10) | Interim Visit 2 | Final Visit (Week 24) |
|--|-----------------------------|----------------------|--------------------------|--------------------|------------------------------|--------------------|--------------------------|
| NBSG Pre-Donation Assessment | X | | | | | | X |
| Informed Consent | X | | | | | | |
| Inclusion and Exclusion Criteria | X | | | | | | |
| Demographics | X | | | | | | |
| Full Blood Count and peripheral blood comment | X | | | X | X | X | |
| Plasma Ferritin | X | | | X | X | X | |
| Malaria Parasites Testing (RDT) | X | X | | X | X | X | |
| Nutritional Counselling | | X | | X | X | X | |
| Qualitative Assessment | | | | | | | X |
| Follow-Up Calls | | | X | | | | |
| Return Blood Donation Status | | | | X | X | X | X |
| Assessment for Adverse Events | | X | X | X | X | X | X |
| Adherence Assessment (for those receiving supplemental iron) | | | X | X | X | X | X |
| RDT – Rapid Diagnostic Test | | | | | | | |

Enrolment

Participants will be re-assessed with their laboratory results at the Day 0 visit.

- ***Eligibility Check***

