Participants will be followed up every 2 months and will be interviewed by members of the research team and appropriate CRFs completed by study staff. Adherence to iron supplementation and nutritional counseling will be assessed biweekly by phone and at each visit.

Participants with suspected adverse events of iron supplementation will be appropriately managed. Participants with suspected bacterial infections will be assessed with blood cultures (if indicated) and tested for malaria parasites during study visits. Malaria preventive measures will be discussed with all study participants on enrolment, and they will be encouraged to use these preventive measures throughout the study. A history of medical events and selected potential adverse events will be obtained at each scheduled visit and during biweekly follow up phone calls. Participants will also be given identification cards to carry with them at all times providing instructions directed to any health care provider who sees them for an unscheduled medical care visit.

- ***Treatment***

The planned duration of treatment is 4 months. Participants with a low plasma ferritin <15 μ g/L, with or without anaemia, will be given oral iron supplementation and nutritional counseling. Treatment will continue for 16 weeks or until the end of follow-up, during which participants will be followed up for adherence counseling at each visit. Clear written instructions for use 3 times a week will be discussed with them. Research staff will contact participants every 2 weeks by phone for adherence and feedback, and to remind participants to keep their scheduled study visits.

Testing of plasma ferritin and FBC after 4 months of supplementation will allow us to assess for response to study treatment with regards to iron stores. After correction of iron depletion or IDA, FBC and plasma ferritin will be monitored at 4 months from baseline. Participants after the end of the intervention phase still found to be iron deficient or anaemic will continue management and further evaluation at the haematology clinic.

- **Discontinuation**

If discontinuation of study treatment occurs, the investigator should make a reasonable effort to understand the primary reason for the participant's premature discontinuation of study treatment and record this information.

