The parallel group's component is designed as a non-inferiority trial for haemoglobin levels at 4 months. At baseline, the 2 groups will be determined based on the need for iron supplementation: all individuals with ID, IDA or low haemoglobin (gender specific values), who satisfy our eligibility criteria regardless of deferral status, will receive iron supplements while all others will not. While a high prevalence of ID and IDA is expected, enrolment will be staggered so that an equal number of participants from each group are enrolled from each site with at least 1 participant who is assigned to iron supplementation. If there are more potential participants in one group at some site, randomization will be used to select the individuals to enroll in the trial to maintain balance over time. The extent of adherence is a central question for this study, and it is also unclear if the haemoglobin deficiency can be improved above what is seen in the control group, hence it is not hypothesized that those receiving iron supplementation will have higher levels of haemoglobin at 4 months. The hypothesis about the iron supplementation intervention is that it will improve haemoglobin levels to near that seen among those who did not receive iron supplementation. If haemoglobin levels are higher in those receiving iron supplementation the intervention would also be deemed a success. Hence a non-inferiority trial is most appropriate for this hypothesis.

Selection of the margin is a critical component of a non-inferiority trial. Here, we specify a margin of 1 g/dL for haemoglobin levels at 4 months. Under a collection of reasonable assumptions, this margin will ensure that the majority of those with low haemoglobin at screening will have haemoglobin levels at 4 months above the threshold for anaemia and should therefore qualify as donors. To see this, assume that half of donors are anaemic at screening (using the thresholds for anaemia of 13 g/dL for men and 11.5 g/dL for women). A simple calculation finds that if we assume haemoglobin levels are normally distributed (which is a reasonable assumption based on observed distributions for haemoglobin in unselected individuals in West Africa) and the standard deviation of screening haemoglobin levels is 1.89 g/dL (this estimate will be described below) then the mean haemoglobin level among men who are deferred is 11.5 g/dL and the mean haemoglobin level among men who are not deferred is 14.5 g/dL (these values for

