## 4 Administration of Study Treatment

Potential first-time donors will be asked if they are interested in participating in a study of the prevalence of ID and IDA and the impact of iron supplementation on haemoglobin levels and repeat donation. Those who express interest, consent to the study, and are eligible will be asked to return within 3 weeks. During this 3-week period a FBC, a peripheral blood film analysis, and a plasma ferritin measurement will be conducted, and participants will be classified as iron supplement participants (e.g., anaemic, ID, IDA) or otherwise (which we refer to as controls in this protocol).

Those found to be anaemic, ID or IDA will receive oral iron supplementation and nutritional counselling. The oral iron supplements will be ferrous sulphate 200mg (65mg Elemental iron). The iron supplements are already available at the Korle-Bu Teaching Hospital Pharmacy. The study principal investigators and study pharmacist will ensure the medicine is stored properly and dispensed only when needed for study participants. The following will be monitored and completed on a periodic basis to ensure the medicine is within study guidelines, pharmaceutical compliance, and manufacturer guidelines:

Drug Accountability Record.

Iron supplement Safety and Handling Sheet.

Controls will not be given iron supplementation at enrolment but will receive the standard practice of nutritional counselling for blood donors. If someone not given iron supplements at enrolment is found to be anaemic, ID or IDA at a follow-up visit that individual will receive iron supplements.

All study participants will have nutritional counselling, dietary advice, and for those

receiving iron, the need for iron therapy to be used consistently 3 days a week.

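### An anaemic donor with normal ferritin is a control under the protocol's entry rule and an iron recipient under the SAP's

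*Protocol*

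**What the plan says.** **Protocol, entry rule.** Methodology (Design): "all individuals with ID or IDA, who satisfy our eligibility criteria regardless of deferral status, will receive iron supplements while all others will not". Under Regimen, "participants will be classified as ID, IDA or otherwise (which we refer to as controls in this protocol". Under Treatment, participants with plasma ferritin below 15 µg/L, "with or without anaemia, will be given oral iron supplementation and nutritional counseling". On definitions, "screened participants will be classified by the WHO criteria as shown in Table 4", and all three rows of that table require ferritin below 15 µg/L.

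**SAP, entry rule.** Section 1.2 (Design): "all individuals with ID, IDA or low haemoglobin (gender specific values), who satisfy our eligibility criteria regardless of deferral status, will receive iron supplements". Section 4: "Those found to be anaemic, ID or IDA will receive oral iron supplementation and nutritional counselling".

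**Protocol text that assumes non-anaemic comparators.** The hypothesis sets treated donors against others, "compared to those who were not deferred with normal haemoglobin". The margin argument takes a control mean from donors above the anaemia threshold: "the mean haemoglobin level among men who are not deferred is 14.5 g/dL". The null hypothesis (Sample size justification; repeated in SAP 2.4) contrasts people with and without low haemoglobin at entry.

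**Later rules.** Protocol, Follow Up Assessments, offers iron to previously untreated participants whose haemoglobin is low at a study visit, even if ferritin is normal. The primary analysis (Protocol, Quantitative Data Analysis; SAP 7.2.1) drops controls who start iron in follow-up because ferritin or haemoglobin changed. It calls for alternative approaches if more than 10% of controls start iron.

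**The concern.** Iron is allocated by clinical status, not by randomisation, so the entry rule is the definition of the arms. If sites follow the protocol, some donors who are anaemic but not iron deficient enter a control group that the hypothesis, the margin argument and the null all treat as non-anaemic.

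Those donors are refused iron at entry and then offered it at the 2-month visit for the same low haemoglobin. Their place in the primary analysis is then unclear. The exclusion is worded for iron started because a value changed, and for them nothing need have changed. They may be kept or dropped depending on how that clause is read. They also count towards the 10% trigger although they are not incident cases.

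**Working it through.** **1. The two rules side by side.** The trial excludes haemoglobin below 10 g/dL, so the affected donors are those from 10 g/dL to the sex cut-off (Table 4: 13.0 g/dL men, 11.5 g/dL women) with ferritin of 15 µg/L or more. Example: a man with haemoglobin 12 g/dL and ferritin 40 µg/L is a control under the protocol and receives iron under the SAP.

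**2. The SAP difference is consistent.** The SAP repeats the wider rule in 1.2 and 4. In 2.4 its allowance for later iron covers incident anaemia, ID or IDA, where the protocol's covers incident ID or IDA only. This is unlikely to be a slip.

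**3. Sample size.** With margin 1.0, SD 1.89, true difference -0.3, one-sided alpha 0.025 and power 85%:

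n per arm = 2 × (1.960 + 1.036)² × 1.89² / (1.0 - 0.3)² = 130.9, so 131. Then 262 / 0.90 = 291.1, so 292 (146 per arm).

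Both stated figures reproduce. The formula does not use the entry rule, so 292 does not depend on which rule is chosen.

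**4. Share of protocol controls who are anaemic but not ID.** Inputs: anaemia prevalence *a* is 48% (unpublished study of 150 donors, Problem Statement) or 18.8% (peri-urban men, same section). ID among anaemic donors *f* is 86.1%, or 63.9% if the IDA figure is used. Under Table 4 an anaemic donor with low ferritin has IDA by definition, so two different percentages of the same anaemic group cannot both follow that table; both are run. ID overall is either *af*, meaning no ID in non-anaemic donors (which is how the protocol reaches 41.3%), or 68.8% (the second unpublished study).

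Share = *a*(1 - *f*) / (1 - ID overall).

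| Scenario | *a* = 48% | *a* = 18.8% |
|---|---|---|
| A: *f* = 86.1%, ID only in anaemic donors | 0.0667/0.587 = 11.4% | 0.0261/0.838 = 3.1% |
| B: *f* = 86.1%, ID overall 68.8% | 0.0667/0.312 = 21.4% | 0.0261/0.312 = 8.4% |
| C: *f* = 63.9%, ID only in anaemic donors | 0.173/0.693 = 25.0% | 0.0679/0.880 = 7.7% |

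These are scenarios, not bounds. Pairing 63.9% with 68.8% would give 0.173/0.312 = 56% at 48% anaemia. It would also require ID to be commoner in non-anaemic donors, (0.688 - 0.307)/0.52 = 73%, than in anaemic ones, so it is set aside.

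**5. Against the trigger.** 10% of 146 is 14.6, so 15 controls starting iron exceed it. If every affected donor stayed low and took iron (an upper case), the 48% column gives about 17, 31 and 36 of 146, and the 18.8% column about 5, 12 and 11.

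**6. What moves these figures.** The exclusion below 10 g/dL lowers them. With mean haemoglobin at the cut-off and SD 1.89, it removes 2Φ(-3.0/1.89) = 11% of anaemic men and 2Φ(-1.5/1.89) = 43% of anaemic women. The 48% column then becomes 7-10%, 13-19% and 16-23% for A, B and C, from all women to all men. Recruiting copper sulphate failures disproportionately (SAP 1.2, Stratification and Sampling) raises them by an amount that the documents do not allow one to calculate.

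**The case against.** The best defence is that the SAP is simply the later document. SAP 1.1 allows it to be modified ahead of the protocol and says that a table after the title page will list changes. A reader might infer that the plan nowhere reconciles the two rules. That cannot be asserted, because the front matter that would hold the table is not in the text available here. Even so, a SAP change table would not amend the protocol, which is the document that governs dosing.

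A reader might also infer that the analysed arms are undefined. They are not: SAP 7.2 analyses people by the iron assigned at enrolment. The open question is who should be assigned it.

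A third inference is that anaemic controls pull down the control mean and so make non-inferiority easier to show. The primary model adjusts for screening haemoglobin, sex and age, so a minority of low-haemoglobin controls is partly accounted for. The 10% trigger and the sensitivity analyses that retain participants who start iron later (Protocol, Quantitative Data Analysis; SAP 7.2.3) limit the effect further. These defences stand as mitigation, but none of them settles allocation at entry.

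**Conclusion.** The inconsistency is real, and it sits in the rule that forms the arms. It should be corrected, but it does not invalidate the analysis, and its effect on the result is not established.

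The wording conflict is certain; its size is not. The answer turns mainly on anaemia prevalence. The 48% comes from one small unpublished donor study. The 18.8% comes from men in the general population, while the protocol expects well over half of donors to be men. It would be tempting to say that the affected donors alone will breach the 10% trigger. The documents do not support that: at 18.8% all three scenarios fall below it, and at 48% all three exceed it before the haemoglobin exclusion but only B and C clearly do so after it.

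**What to change.** - **Entry rule.** Amend the protocol's Design, Regimen and Treatment text to the SAP rule: iron for ID, IDA or low haemoglobin. This rule agrees better with the protocol's hypothesis, margin argument, null and follow-up rule.
- **Cut-offs.** State them once, identically, in both documents. The SAP gives no values for allocation, only a reference to sex-specific ones, and the protocol uses both 11.5 and 12 g/dL for women (Table 4 against the copper sulphate threshold and the mild-anaemia definition). The protocol's own ferritin below 15 µg/L, and haemoglobin 13.0 g/dL for men and 11.5 g/dL for women, would serve. Use the same values in Follow Up Assessments and SAP section 4.
- **Group definitions.** Both documents' margin discussions say that a haemoglobin threshold defines the groups, and both state the null in those terms. Restate these as iron assigned at enrolment versus not, because non-anaemic ID donors are in the iron arm under either rule. Add incident anaemia to the protocol's sample size allowance, as in SAP 2.4.
- **If the ferritin-only rule is preferred,** change SAP 1.2 and 4 instead. Then state how controls who are anaemic at entry are handled at follow-up and whether the primary-analysis exclusion applies to them.

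**Cost.** A protocol amendment with ethics review, because it changes who receives study iron. Some anaemic donors who are not iron deficient would be given iron: 1 - 0.861 = 13.9% of the iron arm (about 20 of 146) if 86.1% of anaemic donors are ID and no non-anaemic donors are, or 36.1% on the 63.9% figure. Moving every low-haemoglobin donor into the iron arm also reduces the haemoglobin overlap between arms on which the covariate adjustment relies. No new data are needed, and the total stays at 292.
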